#### 1. Primary Patency Through 12 months Post-AVF Creation:

Defined as freedom from access thrombosis or any intervention designed to facilitate, maintain or re-establish patency measured from time of access creation through 12 months.

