#### Endpoint Definition:

Primary patency is defined as freedom from access thrombosis or any intervention designed to facilitate, maintain or re-establish patency in a thrombosed access from time of access creation. Subsequent to completion of the AVF creation procedure, consistent with the Training Manual for this staged procedure, the site investigator will assess if an additional PTA balloon maturation or other procedure is needed to promote maturation when outflow is <400 ml/min. Therefore, these specific maturation procedures will not be included in the primary patency endpoint.

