**Endpoint Definition:**

Assisted primary patency is defined as freedom from access thrombosis from time of access creation.

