4.2.1 Secondary Endpoints

The following secondary endpoints to be evaluated in this study are as follows:

1. Primary patency through 12 months post-AVF creation:

Defined as freedom from access thrombosis or any intervention designed to facilitate, maintain or reestablish patency measured from time of access creation through 12 months.

2. Assisted primary patency through 12 months post-AVF creation:
Defined as freedom from access thrombosis from time of access creation through 12 months.
3. Secondary procedure Rate:
Defined as the percentage of subjects having one or more surgical or percutaneous interventions designed to mature or maintain the AVF or re-establish flow. Secondary procedures are procedures subsequent to completion of the AVF creation procedure. This endpoint will also be summarized by type of procedure, indication, procedure success and association with any adverse events (AEs).
4. Overall patient safety:
A full characterization of all adverse events during the study.

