7.7.2 Secondary Objective #1

Primary Patency through 12 months post AVF creation

Analysis Dataset:

Treated Analysis Set per section **Error! Reference source not found..**

Analysis Method:

Primary patency will be summarized for the Treated population using a Kaplan-Meier curve through at least 12 months. Analyses will include patency/survival probabilities and 95% confidence interval bands through the 12-month visit. The confidence interval will be calculated using a typical transformation of the survival function: $\log(S(t))$. Subjects not completing the study will be censored after their last available patency assessment. A sensitivity analysis shall be performed where a cumulative incidence curve is estimated and death will be accounted for as a competing risk. The cumulative incidence curve will be descriptively compared to $1-S(t)$ where $S(t)$ is the survival function estimated by the Kaplan-Meier method.

The observed cumulative incidence estimate may be calculated using the “cmprsk” library in R, with code similar to the following:

```
cmpout1 <- cuminc(time,event)
```

The event variable is 0 if censored, 1 if an event occurs and 2 if a death occurs. Similar analysis will be conducted on the subcomponents of the endpoint.

Endpoint Definition:

Primary patency is defined as freedom from access thrombosis or any intervention designed to facilitate, maintain or reestablish patency in a thrombosed access from time of access creation. Subsequent to the completion of the AVF creation procedure, consistent with the Training Manual for this staged procedure, the site investigator will assess if an additional PTA balloon maturation or other procedure is needed to promote maturation when outflow is <400 ml/min. Therefore, these specific maturation procedures will not be included in the primary patency endpoint. For time-to-event analysis, day 0 is time of access creation and final date is day of event or day of last follow-up. The definition of primary patency is derived from reporting standards by Sidawy, et al and Shenoy, et al [1,2].

Additional Analysis:

- Primary patency post- surgical or endovascular intervention

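### Primary patency is defined differently in the endpoint lists and in the analysis sections, and no planned output shows it without the maturation-procedure exemption

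*Protocol*

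**What the plan says.** Primary patency is defined in four places, which fall into two pairs.

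- **Endpoint lists.** Protocol 4.1.4 counts thrombosis or "any intervention designed to facilitate, maintain or re-establish patency measured from time of access creation through 12 months". SAP 4.2.1 matches it apart from a hyphen: "any intervention designed to facilitate, maintain or reestablish patency measured from time of access creation through 12 months". Neither has an exemption.
- **Analysis sections.** Protocol 13.3.1 counts thrombosis or "any intervention designed to facilitate, maintain or re-establish patency in a thrombosed access from time of access creation", and SAP 7.7.2 has "any intervention designed to facilitate, maintain or reestablish patency in a thrombosed access from time of access creation". Both then say that the site investigator will assess whether a further balloon maturation or other procedure "is needed to promote maturation when outflow is <400 ml/min", and conclude: "Therefore, these specific maturation procedures will not be included in the primary patency endpoint".

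For this endpoint the plan provides a Kaplan-Meier curve, a sensitivity analysis with death as a competing risk, and primary patency after surgical or endovascular intervention. The SAP adds one more item: "Similar analysis will be conducted on the subcomponents of the endpoint".

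The neighbouring endpoint is narrower (Protocol 13.3.2, SAP 7.7.3): "Assisted primary patency is defined as freedom from access thrombosis from time of access creation".

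**The concern.** A section that gives detail may sharpen a summary definition, but here it removes an event that the summary includes. A procedure done to facilitate patency ends primary patency under Protocol 4.1.4 and SAP 4.2.1. A procedure done to promote maturation at low outflow does not end it under Protocol 13.3.1 and SAP 7.7.2. SAP 7.9 records no changes to planned analysis, so the reader is not alerted.

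The thrombosed-access qualifier adds a second ambiguity. If it governs the whole phrase, an intervention counts only once the access has thrombosed, and thrombosis is already an event. The intervention component would then add almost nothing.

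The exemption rests on a site judgement. The text supplied gives a flow threshold but no end date, no limit on number, and no statement of which flow reading applies. The Training Manual and the mapping file named in SAP 10.1 are not supplied and may settle this.

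In a descriptive study the reported percentage is the result. A reader who takes the definition from the endpoint list would misread the curve, and nothing planned would show by how much.

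**Working it through.** **1. The plan's own figure.** Protocol 13.5 and SAP 6 aim for 100 evaluable subjects with 25% drop-out: 100 / 0.75 = 133.3, rounded up to 134. This reproduces, and nothing below changes it.

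**2. Does any planned output lift the exemption?**

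| Planned output | Lifts the exemption? |
|---|---|
| Kaplan-Meier curve (Protocol 13.3.1, SAP 7.7.2) | No; uses the exempted definition |
| Death as competing risk | No; changes only the handling of death |
| Subcomponents (SAP 7.7.2) | No; splits the endpoint as defined |
| Primary patency after intervention | No |
| Secondary Objective #3 (Protocol 13.3.3, SAP 7.7.4) | Counts maturation procedures, but is not time to event and omits thrombosis without a procedure |
| End-of-study AVF status (SAP 10.2) | Last known status only, and optional |

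**3. How far apart can the two definitions be?** Let P be 12-month patency with the exemption and m the share of subjects with at least one exempted procedure. The documents give neither for this study, so both are assumptions. A subject is event-free without the exemption only if event-free with it and free of exempted procedures. Ignoring censoring, the no-exemption value therefore lies between max(0, P − m) and min(P, 1 − m). With P = 70%:

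| m | Lower limit | Upper limit |
|---|---|---|
| 0% | 70% | 70% |
| 10% | 70 − 10 = 60% | min(70, 90) = 70% |
| 30% | 70 − 30 = 40% | min(70, 70) = 70% |
| 50% | 70 − 50 = 20% | min(70, 50) = 50% |
| 70% | 70 − 70 = 0% | min(70, 30) = 30% |

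The gap starts at zero and can be large. Its position within each range depends on whether the same subjects have exempted procedures and counted events.

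**4. Can the zero-procedure share from Secondary Objective #3 stand in?** Take constant hazards over 360 days, drop-out 25%, thrombosis-free 0.85, event-free 0.70 and no exempted procedures (all assumed except the 25%). Let L be the cumulative procedure hazard and D the cumulative drop-out hazard, with D = −ln 0.75 = 0.2877. The crude share with no recorded procedure is 1 − L/(L + D) × (1 − exp(−(L + D))).

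- Every thrombosis treated: L = −ln 0.70 = 0.3567. Share = 1 − (0.3567/0.6444) × (1 − 0.525) = 0.737, which is 3.7 points above 0.70.
- No thrombosis treated: L = −ln(0.70/0.85) = 0.1942. Share = 1 − (0.1942/0.4818) × (1 − 0.6176) = 0.846, which is 14.6 points above 0.70.

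With 25%, 50% and 75% of subjects having an exempted procedure, simulation (134 subjects, 2,000 runs, exempted procedures independent and uniform on Days 14 to 90) gave gaps of 12.0, 9.3 and 6.7 points when no thrombosis is treated. The crude share is thus about 4 to 15 points too high, depending mainly on how many thromboses are treated.

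**The case against.** The strongest reply is that the governing definition is identifiable and openly stated. SAP 10.1 points to Section 7 for endpoint definitions, and Protocol 13.3.1 and SAP 7.7.2 carry the same exemption, so the two documents agree on what will be computed. That stands. The defect is a mismatch between the list and the operative text, present in both documents; it is not a disagreement between Protocol and SAP.

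The exemption is also prespecified and reasoned: creation is staged, and a flow threshold is named. That stands too, and is why the main curve should keep it.

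A reader might infer that maturation work is hidden. It is not. The Table 6 note in Protocol 11.4 says these procedures will be designated on the Secondary Procedure Form. Secondary Objective #3 reports them by type and indication, with rates in person-years that allow for unequal follow-up. Those outputs show how much was done, but not the probability of remaining free of both thrombosis and intervention.

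A reader might also infer that primary patency has become assisted primary patency. The documents do not support that as the intended meaning. One does not maintain patency in an access that has thrombosed, and the exemption would be pointless if interventions in a non-thrombosed access never counted. The wording still permits the literal reading and should be repaired.

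Finally, a reader might take the 99% in the Table 6 note and conclude that no-exemption patency would be about 1%. That does not follow. The figure does not separate index ballooning from later procedures, and index ballooning is not a secondary procedure here (Protocol 9.8 and 9.11).

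**Conclusion.** The point holds as a definitional inconsistency with a missing sensitivity analysis. The endpoint lists count every intervention, the operative sections exempt site-judged maturation procedures, and no planned output gives primary patency under the listed definition.

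The size is unknown. With P assumed to be 70%, the two definitions could coincide or differ by tens of points, depending on an exempted share that the documents do not state. The note to Table 6 does expect post-procedure maturation procedures in this study, so a share of zero would be surprising, but no figure can be attached.

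The consequence is limited to one descriptive secondary endpoint. No primary endpoint, hypothesis test or sample size is affected. The change is worth considering; it does not put the study in question.

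**What to change.** 1. In Protocol 13.3.1 and SAP 7.7.2, reword the qualifier so that non-exempt interventions in a non-thrombosed access clearly count. Keep the <400 mL/min exemption for the main curve.
2. Make Protocol 4.1.4 and SAP 4.2.1 match that definition, or cross-refer to it.
3. Add one sensitivity Kaplan-Meier curve that counts every intervention after the index procedure.
4. Report the number and timing of exempted procedures.

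The cost is a wording change, one curve and one small table. The data on secondary procedures, including type, indication and timing, are already collected, and visits and enrollment are unchanged. The drawback is that the no-exemption curve may be low. It needs a note that planned staged maturation is not device failure.

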#### Analysis Method:

Primary patency will be summarized for the Treated population using a Kaplan-Meier curve through at least 12 months. Analyses will include patency/survival probabilities and 95% confidence interval bands through the 12-month visit. Subjects not completing the study will be censored after their last available patency assessment. A sensitivity analysis shall be performed where a cumulative incidence curve is estimated and death will be accounted for as a competing risk.

## Determination of Subjects/Data for Analysis:

Treated Analysis Set

**Medtronic Business Restricted**

**CONFIDENTIAL**

056-F275 Rev E Clinical Investigation Plan Template

**Additional Analysis:**

Primary patency post-surgical or endovascular intervention

**13.3.2 Secondary Objective #2**

*Assisted Primary Patency through 12 months post AVF creation*

**Endpoint Definition:**

Assisted primary patency is defined as freedom from access thrombosis from time of access creation.

**Analysis Method:**

Assisted primary patency will be summarized for the Treated population using a Kaplan-Meier curve through at least 12 months. Analyses will include patency/survival probabilities and 95% confidence interval bands through the 12-month visit. Subjects not completing the study will be censored after their last available visit. A sensitivity analysis shall be performed where a cumulative incidence curve is estimated and death will be accounted for as a competing risk.

**Determination of Subjects/Data for Analysis:**

Treated Analysis Set

**13.3.3 Secondary Objective #3**

*Rate of Secondary Procedures*

**Endpoint Definition:**

Secondary procedures are surgical or percutaneous interventions designed to mature or maintain the AVF or re-establish flow. Secondary procedures are procedures subsequent to completion of the AVF creation procedure.

**Analysis Method:**

Secondary procedure rate will be summarized cumulatively through 12 months as the number of procedures per person-years as well as the number and percentage of subjects having one or more procedures in the Treated population. This summary will be presented overall and by type of procedure (surgical or percutaneous). Additionally, the number of secondary procedures will be summarized categorically as the number and percentage of subjects with 0, 1, 2, 3, or 4 or more procedures.

Summaries specific to PTA/balloon maturation interventions will be provided. These summaries will be based on secondary procedures that include a PTA/balloon maturation intervention, whether performed alone or in combination with other interventions. The summaries will be presented for interventions performed post-AVF creation through 12 months. The summaries will include the number of PTA interventions performed, whether the PTA was performed in combination with other interventions, the rate of intervention in person-years, the location and average balloon size. Similar summaries will be provided for stent, embolization, and valvulotomy interventions, presented cumulatively through 12 months.

***Medtronic Business Restricted***

This endpoint will also be summarized by type of procedure (e.g. banding, balloon maturation, transposition/elevation/ superficialization, etc.), indication (due to stenosis, due to AE, etc.), procedure success and association with any AEs.

## Determination of Subjects/Data for Analysis:

Treated Analysis Set

## Additional Analysis

- The association between the occurrence of acute anastomotic disruption or pseudoaneurysm and the secondary procedure rate for the Treated population. The mean number of secondary procedures will be summarized cumulatively and stratified by subjects who experienced anastomotic disruption or pseudoaneurysm and those who did not.
- The association between the occurrence of early occlusions and the secondary procedure rate for the Treated population. The mean number of secondary procedures will be summarized for subjects who experienced an early occlusion and those who did not.

### 13.3.4 Secondary Objective #4

*Overall Patient Safety*

#### Endpoint Definition:

All adverse events related to the device, procedure, secondary procedures to maintain or re-establish patency, or any serious adverse event shall be reported. An independent CEC will assess and adjudicate any potential relationship to the device and/or procedures per the criteria set in the CEC charter. Stenosis events will be reported based on the MedDRA terms AVF site stenosis or AVF occlusion.

#### Analysis Method:

Secondary AEs occurring during the study will be presented for the Safety population cumulatively and for each of the following study intervals:

Peri-operative: within 7 days ( $\leq 7$  days) of the AVF creation procedure

Post-operative: 8 days to 3 months after the AVF creation procedure

Follow-up: more than 3 months after the AVF creation procedure

AEs will be summarized as the number of events as well as the number and percentage of subjects experiencing one or more of the following event types:

- Any study-related AE:
  - Cumulative
  - Peri-operative
  - Post-operative
  - Follow-up
- SAE

**Medtronic Business Restricted**

**CONFIDENTIAL**

056-F275 Rev E Clinical Investigation Plan Template

- UADE
- AE related to:
  - study device
  - study procedure
  - intra-procedure or planned balloon angioplasty (PTA) maturation procedures
- Cannulation-related AE
- AE resulting from or related to a secondary procedure
- Stenosis

SAE incidence will be summarized by system organ class and event as the number of events as well as the number and percentage of subjects experiencing each event. These summaries will be presented cumulatively and for each study interval. Non-SAE will be presented in manner similar to SAE.

#### **Determination of Subjects/Data for Analysis:**

Safety Analysis Set

#### **Additional Analysis:**

To assess the safety of the AVF creation procedure, rates for SAEs, UADEs, and procedure-related AEs will be descriptively compared to the pre-market study (DEN170004) results by presenting the rate and 97.5% CI for each study (CI adjusted for multiple comparisons). This comparison will be presented for the peri-operative and post-operative study intervals. If there are differing representations of baseline characteristics between the two studies, they will be adjusted for in the analysis.

### **13.4 Ancillary Objective(s)**

Ancillary objectives include descriptive analyses of ancillary endpoints as well as clinical utility measures. No formal statistical test procedures are planned.

#### **13.4.1 Ancillary Objective #1**

*Functional Patency Rate Through 12-months*

##### **Endpoint Definition:**

Defined as freedom from access abandonment from the time from two-needle cannulation.

##### **Analysis Method:**

Functional patency will be summarized for the Treated population using a Kaplan-Meier curve through at least 12 months. Analyses will include patency/survival probabilities and 95% confidence interval bands through the 12-month visit. Subjects not completing the study will be censored after their last available visit.

#### **Determination of Subjects/Data for Analysis:**

Treated Analysis Set

***Medtronic Business Restricted***

**CONFIDENTIAL**

056-F275 Rev E Clinical Investigation Plan Template

## 13.4.2 Ancillary Objective #2

*Physiological Maturation Rate at 3-, 6-, and 12-months*

### Endpoint Definition:

Physiological maturation is defined in an access site as access vessel minimum blood flow rate  $\geq$  500mL/min and minimum diameter  $\geq$  5mm as measured by duplex ultrasound.

### Analysis Methods:

Physiological maturation will be summarized as the number and percentage of subjects achieving the endpoint along with exact two-sided 95% confidence limits for the percentage, calculated via the Wilson method. The endpoint will be summarized at 3, 6, and 12 months.

### Determination of Subjects/Data for Analysis:

Treated Analysis Set

## 13.4.3 Ancillary Objective #3

*Functional Cannulation Success Through 12-months*

### Endpoint Definition:

Functional cannulation is defined as the time to achieve successful use of the endovascular AVF, with two-needle access and at least two hours of dialysis through the access, for more than two-thirds of the dialysis sessions over a continuous 28-day period after access creation.

### Analysis Methods:

Functional cannulation success will be summarized for the Treated population using a Kaplan-Meier curve through at least 12 months. Analyses will include probabilities and 95% confidence interval bands through the 12-month visit. Subjects not completing the study will be censored after their last available visit.

### Determination of Subjects/Data for Analysis:

Treated Analysis Set

## 13.4.4 Ancillary Objective #4

*Days of Central Venous Catheter Exposure Through 12-months*

### Endpoint Definition:

Days of CVC exposure through 12 months.

### Analysis Methods:

CVC use and exposure during the study will be summarized descriptively for subjects in the Safety population. The summary will include the number and percentage of subjects with CVC use during the study, broken down as:

- CVC present at study procedure

**Medtronic Business Restricted**

- CVC placed prior to AVF maturation
- Additional CVC placed during the study

The overall CVC exposure in days will be summarized descriptively.

## **Determination of Subjects/Data for Analysis:**

Safety Analysis Set

### **13.4.5 Ancillary Objective #5**

*Subject Satisfaction using the Vascular Access Questionnaire (VAQ) at 6 months*

#### **Endpoint Definition:**

Subject satisfaction with the AVF is assessed at the 6-month visit using the Vascular Access Questionnaire (VAQ), a series of 17 questions measuring how much subjects are bothered by problems related to their primary vascular access. Responses range from 0 (Not at all) to 4 (Extremely) and the VAQ summary score ranges from 0 to 68 with higher values indicating more negative views of vascular access.

#### **Analysis Methods:**

The VAQ will be summarized for subjects in the Treated population whose primary access is the study AVF. Summaries will present the number and percentage of subjects not bothered by any symptoms and the number and percentage of subjects at least moderately bothered by each symptom. Descriptive statistics for the overall VAQ score will be provided.

## **Determination of Subjects/Data for Analysis:**

Treated Analysis Set

### **13.4.6 Ancillary Objective #6**

*Nurse-Cannulator Satisfaction at 3-, 6-, and 12-months*

#### **Endpoint Definition:**

Cannulator training and experience cannulating the study AVF is assessed at approximately 3, 6, and 12 months post AVF creation.

#### **Analysis Methods:**

Baseline cannulator training will be summarized using the responses from the first study AVF cannulated by each cannulator. Cannulator experience with the study AVF will be presented for the Treated population at each timepoint, summarizing each question descriptively. Missing responses will not be included.

